**Novo Nordisk**

- If the difference of the visit date and the delivery date was  $\leq 35$  days (28 days between scheduled site visits + 7 days visit window = 35 days), LPVISPD L is set to the last visit.
- If the difference of the visit date and the delivery date was  $> 35$  days, LPVISPD L is set to the following planned site visit 4 weeks later.

**Step 4:** For subjects registered to miss site visit 79 due to the Covid-19 pandemic, LPVISPD L is set to 79.

**Step 5:** For subjects withdrawing from trial before GW16 without further information, delivery is assumed to be after GW16 and LPVISPD L is set to 79.

Hence, data assessed at the planned visit prior to delivery will be used in the analysis, provided the visit corresponds to the visit on or after GW 16.

Statistical Analysis Plan  
Trial ID: NN1250-4300  
UTN: U1111-1191-3018  
EudraCT No: 2017-000048-17

~~CONFIDENTIAL~~

Date:	27 January 2021	Novo Nordisk
Version:	2.0	
Status:	Final	
Page:	34 of 34	

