#### 2.4 Trial flowchart for phone contacts in the pregnancy period of the trial

	Additional phone contacts a		Pregnancy period		Postpartum period			Follow-up	Premature discontinuation
	P55ABC	P56-P58	P60-P82	P83-P85 b	P87	P88	P89		
Weekly phone contacts (P) in-between monthly site visits	P55ABC	P56-P58	P60-P82	P83-P85 b	P87	P88	P89	P91 (FU1)	P91A (FU1-A)
Timing of contacts, GW (gestational weeks), d (days)	--	--	GW13-GW39	GW40-GW42	7d after delivery	14d after delivery	21d after delivery	EOT +7d	EOT-A +7d
Visit Window (days)	±3	±3	±3	±3	±3	±3	±3	+5	+5
Premature discontinuation criteria	X	X	X	X	X	X	X		
Withdrawal criteria	X	X	X	X	X	X	X	X	X
Concomitant medication (diabetes)	X	X	X	X	X	X	X	X	X
Concomitant medication (other)	X	X	X	X	X	X	X		
2-point profile	X	X	X	X	X	X	X		
Adverse events	X	X	X	X	X	X	X	X	X
Hypoglycaemic episodes	X	X	X	X	X	X	X	X	X
Technical complaints	X	X	X	X	X	X	X	X	X
Pregnancy outcome					X	X	X		
Infant health status					X	X	X	X	
New dose of trial insulin	X	X	X	X	X	X	X		
Dose of trial insulin	X	X	X	X	X	X	X		

a The additional phone contacts P55A-P55C are applicable for subjects randomised pregnant before GW 12 or for subjects that were randomised non-pregnant and become pregnant in the conception period of the trial and have an ultrasound scan completed before GW 12. The additional phone contacts P56-P58 are to be completed as needed until visit 59 can be completed in GW 16.

b The phone contacts P83-P85 are only applicable for subjects with delivery after GW 40.

Protocol  
Trial ID: NN1250-4300  
UTN: U1111-1191-3018  
EudraCT no.: 2017-000048-17

CONFIDENTIAL

Date: 17 December 2020  
Version: 4.0  
Status: Final  
Page: 23 of 110

Novo Nordisk

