**Novo Nordisk**

Pregnant subjects discontinuing treatment prematurely should hereafter attend all remaining planned visits of the trial. If applicable, the phone contacts should preferably be completed weekly in order to maintain glycaemic control.

For subjects not able or willing to attend all planned site visits, these can be converted to phone contacts. Efforts should be made to ensure collection of the scheduled 9-point profiles as per flowchart Section 2.3 and attendance at the most important key visits, i.e. visit 79 for collection of an HbA1c sample prior to delivery, the delivery visit, the end of treatment visit V90 (except 2-point profile), and the originally scheduled V92 follow-up visit. The key visits to be completed for subjects discontinuing treatment prematurely are summarised in [Figure 8-2](#).

Abbreviations: V2 = pregnancy baseline visit (ultrasound scan), EOT = end of treatment (V90), FU2 = follow-up visit 2 (V92), EOT-A = additional end of treatment (V90A), FU1-A/FU2-A = additional follow-up contacts 1 (P91A) and 2 (V92A), V79 = gestational week 36, D = delivery (V86).

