#### 17.3.1 Primary analysis for the primary estimand

The primary estimand will be estimated based on the FASpregnant using data from the last planned visit prior to delivery after GW 16. Hence, data assessed at the planned visit prior to delivery will be used in the analysis, provided the visit corresponds to the GW 16 visit or later. If delivery is in GW 40, data from GW 36 will be used. If data at this visit is missing, and data from an additional visit after GW 36 and prior to delivery is available, data from this visit will be used. Similarly, if delivery is in week GW 18, data from GW 16 will be applied. If data at this visit is missing, and data from an additional visit after GW 16 and prior to delivery is available, data from this visit will be applied. Available data from the in-trial period will be included regardless of whether trial product was discontinued or not.

The primary statistical analysis will be using multiple imputations to handle missing data assuming that the missing data mechanism is missing at random (MAR) within the groups used for imputation.

Imputation of missing data will be done within four groups of subjects defined by randomised treatment arm and whether or not subjects discontinue treatment. It is hereby assumed that the likely values of what the missing data would have been if available, are best described by information

Protocol  
 Trial ID: NN1250-4300  
 UTN: U1111-1191-3018  
 EudraCT no.: 2017-000048-17

~~CONFIDENTIAL~~

Date: 17 December 2020  
 Version: 4.0  
 Status: Final  
 Page: 87 of 110

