**Novo Nordisk**

## 5 Statistical analyses

### 5.1 General considerations

Results from a statistical analysis will at a minimum be presented by the estimated treatment contrasts for the comparison between IDeg and IDet with associated two-sided 95% confidence intervals (CI) and p-values corresponding to two-sided tests of no difference.

Non-inferiority will be considered confirmed if the upper bound of the CI is strictly below 0.4%. The p-value corresponding to a two-sided test of no difference will also be reported.

The full analysis set for all pregnant women (**FASpregnant**) who contribute to the analysis will be used in the analysis of efficacy endpoints. For further details of how the subjects will be determined whether they contribute to the statistical analysis or not refer to [6.3.1.1](#). For the safety endpoints, the safety analysis set for all pregnant women (**SASpregnant**) will be used. The definition of analysis sets are given in section [4](#).

The treatment baseline value will be used in the statistical models and is defined as the latest available measurement at or before randomisation. For all subjects the treatment baseline value hence corresponds to the value obtained at the randomisation visit (visit 2) if available, or at the screening visit (visit 1). If neither of these measurements have been obtained the treatment baseline will be left missing. For subjects randomised pregnant the pregnancy baseline is derived from the treatment baseline, and the two baseline values will be identical, corresponding to the values obtained at visit 2 or visit 1.

When summarising change from baseline for effect and safety variables assessed during or after the pregnancy period, both treatment baseline and pregnancy baseline variables will be applied. First the treatment baseline described above to illustrate changes since initiation of treatment, second the pregnancy baseline to illustrate changes since early pregnancy.

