## 6.3 Appendix 3: Definition and calculation of endpoints, assessments and derivations

### 6.3.1 Endpoint derivations and assessments

#### 6.3.1.1 Steps involved in defining last planned visit prior to delivery after GW 16 (LPVISPD L) :

The 188 subjects who were in full analysis set for pregnant women only qualify for the statistical analysis , hence LPVISPD L will be defined for only these subjects.

**Step 1:** Subjects delivering before GW16 is excluded from the analysis and LPVISPD L is not defined

**Step 2:** For subjects with visit 79 as the last site visit, LPVISPD L is set to 79.

**Step 3:** For subjects with visit 59, 63, 67, 71, or 75 as the last site visit prior to delivery the following is done:

Statistical Analysis Plan  
Trial ID: NN1250-4300  
UTN: U1111-1191-3018  
EudraCT No: 2017-000048-17

~~CONFIDENTIAL~~

Date: 27 January 2021  
Version: 2.0  
Status: Final  
Page: 33 of 34

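### SAP 6.3.1.1 Step 3 moves the primary-endpoint visit on only once, so a woman who misses two or more planned visits gets a visit up to 16 weeks before the one protocol 17.3.1 requires, and some women get none

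*SAP*

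**What the plan says.** **Protocol.** Section 17.3.1 ties the endpoint visit to the timing of delivery. Its example is "If delivery is in GW 40, data from GW 36 will be used", and delivery in GW 18 leads to the GW 16 visit. A discontinuer with no retrieved value and an unknown time of delivery is taken to deliver after GW 16 and is imputed. Section 8.4.4 lets women who stop trial product leave the site visits but stay in the trial: "For subjects not able or willing to attend all planned site visits, these can be converted to phone contacts".

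**SAP 6.3.1.1** has five steps.
- Step 1 leaves out deliveries before GW 16.
- Step 2 assigns V79 when V79 is the last site visit.
- Step 3 begins: "For subjects with visit 59, 63, 67, 71, or 75 as the last site visit prior to delivery the following is done". With 35 days or less to delivery the last visit stands. With more, "LPVISPD L is set to the following planned site visit 4 weeks later". The threshold is explained as "28 days between scheduled site visits + 7 days visit window = 35 days".
- Step 4 assigns V79 when that visit was registered as missed because of Covid-19.
- Step 5 states: "For subjects withdrawing from trial before GW16 without further information, delivery is assumed to be after GW16", and assigns V79.

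The section closes by saying that the planned visit before delivery supplies the data.

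**Links.** SAP 5.1 makes this section settle who is analysed; its words are "how the subjects will be determined whether they contribute to the statistical analysis or not refer to" 6.3.1.1. SAP 5.3.1 and 5.3.2.1 repeat the protocol's rule on discontinuers with unknown delivery. SAP Appendix 2, which lists changes from the protocol, covers only pre-eclampsia and the pregnancy outcome summaries.

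**The concern.** The protocol's rule depends on when a woman delivers. Step 3 depends on when she last came to the site. The two coincide only while the gap is short, because Step 3 advances once and stops. Women who stop attending early are the ones for whom the treatment-policy estimand differs from the adherence estimand, so the rule misfires in the group that the primary estimand is meant to keep.

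The SAP also treats similar women differently. A woman lost before GW 16 gets V79 under Step 5, and one who missed V79 because of Covid-19 gets V79 under Step 4. A woman who attended V59, then lapsed for another reason and delivered at term gets V63.

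At stake are which imputation group a woman joins, and whether women with no assigned visit contribute at all.

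**Working it through.** **Inputs.** V59 is the GW 16 visit (Protocol 2.4: "until visit 59 can be completed in GW 16"). V63, V67, V71, V75 and V79 follow at GW 20, 24, 28, 32 and 36 (Protocol 2.3). The threshold is 28 + 7 = 35 days, as the SAP states.

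**1. The two rules side by side.** Gap in days = (delivery week − week of last site visit) × 7. SAP Step 3 keeps the last visit if the gap is 35 or less and otherwise takes the next one. The protocol takes the latest planned visit before delivery.

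| Last site visit | Gap, delivery GW 38 | Step 3 | Protocol | Weeks early | Gap, delivery GW 34 | Step 3 | Protocol | Weeks early |
|---|---|---|---|---|---|---|---|---|
| V59 (GW 16) | 154 | GW 20 | GW 36 | 16 | 126 | GW 20 | GW 32 | 12 |
| V63 (GW 20) | 126 | GW 24 | GW 36 | 12 | 98 | GW 24 | GW 32 | 8 |
| V67 (GW 24) | 98 | GW 28 | GW 36 | 8 | 70 | GW 28 | GW 32 | 4 |
| V71 (GW 28) | 70 | GW 32 | GW 36 | 4 | 42 | GW 32 | GW 32 | 0 |
| V75 (GW 32) | 42 | GW 36 | GW 36 | 0 | 14 | GW 32 | GW 32 | 0 |

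Delivery in GW 40 assigns the same visits as GW 38. The rules differ only when at least two planned visits before delivery were missed.

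**2. Women whom no step covers.**
- (a) Last site visit before V59 (V2, V55 or V55D) with a known delivery after GW 16. Step 3 starts at V59, and Step 5 is confined to withdrawal before GW 16 without further information.
- (b) Last site visit V59 to V75 with unknown delivery date. Step 3 cannot be evaluated without that date. For discontinuers in (b), SAP 5.3.1 and 5.3.2.1 say they are imputed, so the SAP conflicts with itself.

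**3. How this reaches the estimate.** None of the imputation models in SAP 5.3.2.1 has a gestational-week term. A woman with no HbA1c at either visit therefore has the same imputed mean at GW 20 as at GW 36 unless her imputation group changes. SAP 5.3.2.1 describes the groups first by whether a woman discontinues, then by her status at the last scheduled visit before delivery. On the second description, a woman on trial product at GW 20 and off it by GW 36 changes group.

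**4. A ceiling on size.** The SAP gives 188 women in the full analysis set. With the protocol's 10% delivering before GW 16, 188 × 0.9 = 169 remain. Its 6% missing is 169 × 0.06 ≈ 10 women, and its 12% discontinuing is 169 × 0.12 ≈ 20.

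*Misclassification.* Suppose every missing woman in one arm is put in the wrong group, none in the other arm is, and on- and off-treatment HbA1c differ by d. That arm's mean moves by 0.06 × d. The documents do not give d. Assuming 0.25, 0.5 or 1.0 percentage points gives 0.015, 0.03 or 0.06, against a margin of 0.4.

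*Omission.* A two-sample t calculation (one-sided 2.5%, margin 0.4, true difference 0, 80% power) reproduces the 144 and 162 women in protocol Table 17–1 for SD 0.85 and 0.90. With 169 women, power is 86.1% and 82.0%. With the 6% left out, 169.2 × 0.94 = 159 women remain and power is 83.9% and 79.5%.

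**The case against.** **Exclusion.** A reader might infer that the women in (a) and (b) are dropped. The documents do not say so. Step 1 is the only stated exclusion, the section opens by saying the visit will be defined for the 188 women, and SAP 5.3.1 and 5.3.2.1 impute discontinuers whose time of delivery is unknown. This part stands: the fault is silence and internal conflict, not a declared exclusion. It does not help women in (a), whose delivery is known.

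**V90A as endpoint.** A reader might also infer that an HbA1c from the early-discontinuation visit V90A at about GW 24 would count as the endpoint for a term delivery. That requires Step 3 to ignore V90A as a site visit, and also requires the additional-visit fallback, which appears in protocol 17.3.1 but not in SAP 5.3. If V90A does count as a site visit, Step 3 does not name it and moves nothing. The text does not settle which, so this calls for one clarifying sentence and no more.

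**Imputation group.** If the groups depend on ever having discontinued, an early endpoint visit changes nothing for a woman who stops at GW 24. That is one fair reading. The SAP's next sentence supports the other, so the ambiguity remains.

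**Size.** The 10 to 20 women are all missing or all discontinuing women, not those caught by Step 3. Sites are told to secure V79, and Steps 2, 4 and 5 already send many women there. For the degludec arm, a 0.5 penalty in the tipping-point analysis covers the same 0.03. This stands, although that analysis does not address omitted women.

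**A rule by delivery date alone would cost data.** Take V75 at GW 32+0 and delivery at GW 36+2, 30 days later. The SAP uses the observed value; a strict date rule would assign V79 and impute. This stands, and the fix keeps the 35-day allowance.

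**Conclusion.** The concern holds in a limited form. When two or more planned visits before delivery are missed, Step 3 gives a visit 4 to 16 weeks earlier than protocol 17.3.1 and the section's own closing sentence require for a delivery in GW 38 or 40. The change is not declared in Appendix 2. One missed visit, or a last visit at V75, agrees with the protocol. Groups (a) and (b) have no assigned visit.

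The number of women affected and the effect on the treatment difference cannot be computed from the documents. The effect is probably small against 0.4: the 0.03 figure rests on an assumed 0.5-point difference and on one-sided misclassification of every missing woman in one arm. Nothing here shows that the non-inferiority conclusion would change. It should still be repaired, because in an open-label trial the rule that selects the primary value should be complete and should match the protocol or be declared as a change.

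**What to change.** Amend SAP 6.3.1.1 as follows.

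1. In Step 3, keep advancing in 4-week steps until the gap from that visit's scheduled date to delivery is 35 days or less, or V79 is reached. Last visit V59 with delivery in GW 38 then runs through gaps of 126, 98, 70 and 42 days to V79. One-missed-visit cases do not change.
2. Apply the same rule, starting from V59, to women last seen on site before V59 who delivered after GW 16.
3. Assign V79 to every woman in the pregnant full analysis set whose delivery date is unknown, whatever the time of withdrawal. This agrees with SAP 5.3.1 and 5.3.2.1.
4. If HbA1c is missing at the assigned visit, choose the imputation group by whether trial product had been stopped by that visit's scheduled date.
5. State that V90A and V92A do not count as the last site visit in this derivation.
6. List any remaining departure from protocol 17.3.1 in Appendix 2.

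The cost is a short change to the wording and the derivation. Gestational age, delivery date and last date on trial product are already collected. A few women may move between imputation groups. Since the 188 women are already identified, the sponsor can count those affected and report the number.
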